3.4 BASELINE EVALUATIONS

- 3.4.1 Within 7 Days Prior to the First Vaccination (Day 0)
 - Physical examination, including ECOG (see Appendix B)
 - Weight and vital signs
 - Baseline blood tests:
 - o CBC w/differential
 - Acute Care Panel (sodium, potassium, chloride, bicarbonate, creatinine, glucose, BUN), Hepatic Panel (alkaline phosphatase, AST, ALT, total bilirubin, direct bilirubin), Mineral Panel (albumin, calcium, magnesium, phosphorus), Uric acid, Creatinine kinase, Lactate dehydrogenase, Total protein
 - PT-INR/PTT
 - Anti-CMV antibody titer, HSV and VZV serology, and EBV panel (Note: Patients who are known to be positive do not need to be retested. May be performed within 3 months prior to Part Two registration.)
 - β-HCG pregnancy test (serum or urine) on all women of child-bearing potential
 - Urinalysis, with culture if indicated
 - Chest x-ray
 - EKG
 - Repeat imaging if not performed within 4 weeks of Day 0. This may include CT, MRI, PET, and/or photography.
- 3.4.2 Within 2 Days Prior to the First Vaccination (Day 0)
 - Lymphocyte phenotyping (TBNK)
 - Review of baseline symptoms
 - Research samples, as described in Section 5.3

3.5 **ON-STUDY EVALUATIONS**

- 3.5.1 Within 2 Days Prior to Each Subsequent Vaccination (Days 14, 28, & 42 (± 5 days))
 - Physical examination, including ECOG (see Appendix B)
 - Weight and vital signs
 - Toxicity assessment, including a review of systems
 - CBC w/differential
 - Acute Care Panel (sodium, potassium, chloride, bicarbonate, creatinine, glucose, BUN), Hepatic Panel (alkaline phosphatase, AST, ALT, total bilirubin, direct bilirubin), Mineral Panel (albumin, calcium, magnesium, phosphorus), Uric acid, Creatinine kinase, Lactate dehydrogenase, Total protein

- β-HCG pregnancy test (serum or urine) on all women of child-bearing potential
- Research samples, as described in Section 5.3
- 3.5.2 After Each Vaccination
 - Vital signs will be monitored hourly (± 15 minutes) for two hours. The postadministration monitoring period may be adjusted by the PI.

3.6 POST-TREATMENT (FOLLOW-UP) EVALUATIONS

3.6.1 First Follow-up Evaluation

All patients (unless the patient receives a second course of treatment) will return to the NIH Clinical Center for their first follow-up evaluation on day 56 (\pm 5 days), which is approximately two weeks after the fourth vaccination. If a patient receives a second course of four vaccines, the first follow-up evaluation will be two weeks (\pm 5 days) after the eighth vaccination.

At the first follow-up evaluation, patients will undergo:

- Physical examination, including ECOG (see Appendix B)
- Weight and vital signs
- Toxicity assessment, including a review of systems
- CBC w/differential
- Acute Care Panel (sodium, potassium, chloride, bicarbonate, creatinine, glucose, BUN), Hepatic Panel (alkaline phosphatase, AST, ALT, total bilirubin, direct bilirubin), Mineral Panel (albumin, calcium, magnesium, phosphorus), Uric acid, Creatinine kinase, Lactate dehydrogenase, Total protein
- Lymphocyte phenotyping (TBNK)
- β-HCG pregnancy test (serum or urine) on all women of child-bearing potential
- Research samples, as described in Section **5.3**. Approximately 72 mL of blood will be obtained. PBMC will be cryopreserved so that immunologic testing may be performed. This will be performed on protocol 03-C-0277.
- Imaging studies as performed at baseline to determine tumor response. If clinically indicated, other scans or x-rays may be performed, e.g. brain MRI, bone scan.
- A 5-liter apheresis may be performed. If the patient is unable to undergo apheresis, approximately 96 mL of blood may be obtained. This will be performed on protocol 03-C-0277.

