3.1.3 Treatment Phase

Patients will receive a mRNA-based vaccine IM at two-week intervals for four cycles. All patients may receive one course of treatment (four vaccination cycles). Immunologic tests will be performed as per Section **5.4** to quantitate circulating T-cells reactive with the immunizing antigens. If a 3-fold increase in the precursor level of pre-existing neoantigen-specific T-cells or new reactivity appears in the blood at detectable levels, patients may be vaccinated with a second and final course of treatment using the same vaccine dose. The second course may start approximately four weeks (± 2 weeks) from the last vaccine dose of the first course.

If the patient receives only one course of treatment (four vaccination cycles), the start date of the course will be the date of the first vaccination; the end date will be the date of the first post-treatment evaluation. If the patient receives a second course (four additional vaccination cycles), the start date of the first course will be the date of the first vaccination. The date of the fifth vaccination will be both the end date of the first course and the start date of the second course. The end date of the second course will be the date of the first post-treatment evaluation.

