3.6.2 Subsequent Follow-up Evaluations

All patients will return to the NIH Clinical Center for their second follow-up evaluation one month (± 5 days) after the first follow-up evaluation. Subsequent follow-up evaluations will take place every 1-2 months for the first year, and then annually for up to five years or until clinically proven progressive disease, whichever comes first. Patients will be co-enrolled and followed on the NCI-SB long-term follow-up protocol 09-C-0161 (Follow-up Protocol for Subjects Previously Enrolled on NCI Surgery Branch Studies). As noted in Section **3.6.1**, additional apheresis may be performed only at the first follow-up evaluation. It will not be performed at any other post-treatment evaluations.

Note: Patients may be seen more frequently as clinically indicated. Patients who are unable or unwilling to return for follow-up evaluations may be followed via phone or email contact. Patients may be asked to send laboratory, imaging, and physician exam reports performed by their treating physician.

At each scheduled follow-up evaluation, patients will undergo:

- Physical examination, including ECOG (see Appendix B)
- Weight and vital signs
- Toxicity assessment, including a review of systems
- CBC w/differential
- Acute Care Panel (sodium, potassium, chloride, bicarbonate, creatinine, glucose, BUN), Hepatic Panel (alkaline phosphatase, AST, ALT, total bilirubin, direct bilirubin), Mineral Panel (albumin, calcium, magnesium, phosphorus), Uric acid, Creatinine kinase, Lactate dehydrogenase, Total protein
- Lymphocyte phenotyping (TBNK)
- β-HCG pregnancy test (serum or urine) on all women of child-bearing potential (complete at all follow-up evaluations within 120 days after the last vaccine)
- Research samples, as described in Section **5.3**. Approximately 72 mL of blood will be obtained at each follow-up visit. PBMC will be cryopreserved so that immunologic testing may be performed. This will be performed on protocol 03-C-0277.
- Imaging studies as performed at baseline to determine tumor response. If clinically indicated, other scans or x-rays may be performed, e.g. brain MRI, bone scan.

STUDY ASSESSMENT CALENDAR 3.7

		Screening		Baseline	ine	S-nO	study/Cou	On-Study/Course of Treatment	atment	Doct Two	Doct Turotmont Follow un
	(Prior to Pa	Prior to Part Two registrati	istration)	(Prior to first vaccine)	t vaccine)		(1 vaccin	$(1 \text{ vaccine} = 1 \text{ cycle})^1$	e) ¹	L USU- 116	aunent ronow-up

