3.8 CRITERIA FOR REMOVAL FROM PROTOCOL THERAPY AND OFF-STUDY CRITERIA

Prior to removal from study, effort must be made to have all subjects complete an evaluation safety visit approximately 30 days following the first follow-up evaluation (at the second follow-up evaluation).

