6.2.2 Genomic Data Sharing Plan

The NIH Genomic Data Sharing Policy does not apply to this study.

6.3 **RESPONSE CRITERIA**

For the purposes of this study, patients should be re-evaluated for response approximately two weeks following the last vaccination, then one month later x1, then every 1-2 months for the first

year, and then annually for up to five years or until clinically proven progressive disease, whichever comes first. In addition to a baseline scan, confirmatory scans should also be obtained at least 4 weeks (but not less than 4 weeks) following initial documentation of objective response.

Response and progression will be evaluated in this study using the new international criteria proposed by the revised Response Evaluation Criteria in Solid Tumors (RECIST) guideline (version 1.1)²⁸ Changes in the largest diameter (unidimensional measurement) of the tumor lesions and the shortest diameter in the case of malignant lymph nodes are used in the RECIST v1.1 criteria.

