6.3.3.3 Evaluation of Best Overall Response

The best overall response is the best response recorded from the start of the treatment until disease progression/recurrence (taking as reference for progressive disease the smallest measurements recorded since the treatment started). The patient's best response assignment will depend on the achievement of both measurement and confirmation criteria.

Target Lesions	Non-Target Lesions	New Lesions	Overall Response	Best Overall Response when Confirmation is Required*
CR	CR	No	CR	\geq 4 weeks confirmation**
CR	Non-CR/Non-PD	No	PR	\geq 4 weeks confirmation**

For Patients with Measurable Disease (i.e., Target Disease)

CF	R	Not evaluated	No	PR		
PF	٤	Non-CR/Non- PD/Not evaluated	No	PR		
SE)	Non-CR/Non- PD/Not evaluated	No	SD	Documented at least once \geq 4 weeks from baseline**	
PE)	Any	Yes or No	PD		
An	y	PD***	Yes or No	PD	No prior SD, PR, or CR	
An	ıy	Any	Yes	PD		
 * See RECIST v1.1 manuscript for further details on what is evidence of a new lesion. ** Only for non-randomized trials with response as primary endpoint. *** In exceptional circumstances, unequivocal progression in non-target lesions may be accepted as disease progression. 						
Note : Patients with a global deterioration of health status requiring discontinuation of treatment without objective evidence of disease progression at that time should be reported as " symptomatic deterioration ." Every effort should be made to document the objective progression even after discontinuation of treatment.						

For Patients with Non-Measurable Disease (i.e., Non-Target Disease)

Non-Target Lesions	New Lesions	Overall Response		
CR	No	CR		
Non-CR/Non-PD	No	Non-CR/Non-PD*		
Not all evaluated	No	Not evaluated		
Unequivocal PD	Yes or No	PD		
Any	Yes	PD		
* 'Non-CR/non-PD' is preferred over 'stable disease' for non-target disease since SD is				

* 'Non-CR/non-PD' is preferred over 'stable disease' for non-target disease since SD is increasingly used as an endpoint for assessment of efficacy in some trials; so, to assign this category when no lesions can be measured is not advised.

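### A second-course patient who leaves before the late first scheduled scan (nominally Day 126, against Day 56) drops out of the evaluable denominator, and 3.6.1 leaves Day 56 imaging unclear while the second-course decision is open

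*Combined protocol and SAP*

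**What the plan says.** Section 3.6.1 sets the first follow-up evaluation, which includes response imaging, at Day 56 (±5 days), with an exception: "All patients (unless the patient receives a second course of treatment) will return". For the excepted group, "If a patient receives a second course of four vaccines, the first follow-up evaluation will be two weeks" (±5 days) after the eighth vaccination. Footnote 2 of the calendar in 3.7 repeats this. Section 6.3 uses the same anchor: "patients should be re-evaluated for response approximately two weeks following the last vaccination". The visits before each vaccination (3.5.1) list examinations and blood tests but no imaging.

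Whether a second course is given depends in part on a blood result. If neoantigen-specific T-cells rise 3-fold, or new reactivity appears, "patients may be vaccinated with a second and final course of treatment using the same vaccine dose" (3.1.3). On timing, "The second course may start approximately four weeks" (±2 weeks) from the last dose of the first course.

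Section 8.3.2 defines evaluable for response as measurable disease at baseline, at least one course received, and disease re-evaluated. Section 8.2 applies its two-stage rule to evaluable patients: stop at 0 of 12, positive at 3 or more of 21, with up to 2 inevaluable patients allowed per Phase II cohort. Section 8.4.5 adds an intention-to-treat analysis of all enrolled patients but attaches no decision rule to it.

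**The concern.** Response rate is a primary endpoint, and each cohort is decided by 3 responders among 21. Two features of the schedule bear on that count.

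The first is the denominator. A patient who has completed course 1 has met the treatment requirement of 8.3.2. If that patient goes on to course 2 and then deteriorates, withdraws or starts another therapy before being scanned, the re-evaluation requirement fails and the patient leaves the set. Leaving early for those reasons is far more likely in a non-responder. A comparable one-course patient would have been due a scan two weeks after dose 4.

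The second is the Day 56 scan itself. The exception turns on whether a patient receives a second course, yet dose 5 may come as late as Day 84. On Day 56 the decision may still be open, and the text does not say whether such a patient attends and is imaged. If not, a response present at Week 8 and gone by about Week 18 is seen by no scheduled scan.

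**Working it through.** **Timeline.** Inputs: doses on Days 0, 14, 28 and 42 (3.1.5, 3.3); second course 28 ± 14 days after dose 4, at two-week intervals (3.1.3); first follow-up 14 days after the last dose (3.6.1).

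- One course: 42 + 14 = Day 56, the plan's own figure.
- Dose 5: 42 + 28 = Day 70 (Days 56 to 84 over the start window).
- Dose 8: 70 + 3 × 14 = Day 112 (Days 98 to 126).
- First scheduled scan after two courses: 112 + 14 = Day 126 (Days 112 to 140).
- Delay against one course: 126 − 56 = 70 days (56 to 84), that is 10 weeks (8 to 12).

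These ranges leave out the ±5-day visit window on both sides. With it, the comparison is Days 107 to 145 against Days 51 to 61. Two-week spacing in course 2 is taken from 3.1.3; the plan does not list the second-course days.

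**Decision rule as written.** Inputs from 8.2: 12 patients in stage 1, stop at 0; 21 in total, positive at 3 or more; p0 = 0.05, p1 = 0.20. A cohort is positive if it has at least 3 responses in 21, unless stage 1 had none. So

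P(positive) = P(X ≥ 3 of 21) − (1 − p)^12 × P(Y ≥ 3 of 9).

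- Early stopping at p = 0.05: 0.95^12 = 0.540, which reproduces the plan's 54.0%.
- p = 0.05: 0.0849 − 0.540 × 0.0084 = 0.0804.
- p = 0.20: 0.8213 − 0.0687 × 0.2618 = 0.8033.

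The rule has a type I error of 8.0% and power of 80.3%.

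**Effect of excluded non-responders.** Suppose k patients per cohort complete course 1, start course 2, leave unscanned, and are all non-responders. To fill 21 evaluable places, 21 + k are treated. If the true rate among all of them is 5%, the rate among the evaluable is 0.05 × (21 + k)/21.

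| k | Rate among evaluable | P(X ≥ 3 of 21) | Subtracted term | Type I error |
|---|---|---|---|---|
| 0 | 0.0500 | 0.0849 | 0.0045 | 8.0% |
| 1 | 0.0524 | 0.0946 | 0.0050 | 9.0% |
| 2 | 0.0548 | 0.1047 | 0.0055 | 9.9% |

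The value k = 2 uses the whole allowance in 8.2 for inevaluable patients in a cohort, although that allowance covers every cause of inevaluability.

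**Transient responses.** Confirmation needs at least 4 weeks (6.3). A response present at Day 56 is at risk of being missed if it lasts at least 4 weeks more but less than about 10 (8 to 12 over the start window). No rate can be attached to this band.

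**The case against.** The schedule is internally consistent. Sections 3.6.1, 3.7 and 6.3 all anchor the first response evaluation on the last vaccination, and that is a legitimate choice. Best overall response (6.3.3.3) runs from the start of treatment to progression, and scans continue every 1 to 2 months in the first year, so the endpoint does not rest on one scan. Several passages also make loss without a scan less likely:

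- Under 6.3, a patient who stops in mid-course is due for re-evaluation about two weeks after the dose actually last given; after dose 5 alone, that is nominally 70 + 14 = Day 84.
- Section 3.6.2 allows outside reports: "Patients may be asked to send laboratory, imaging, and physician exam reports performed by their treating physician".
- Section 3.8 says "effort must be made to have all subjects complete an evaluation safety visit approximately 30 days following the first follow-up evaluation".
- The note in 6.3.3.3 says "Every effort should be made to document the objective progression even after discontinuation of treatment".

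All of this stands. It makes the excluded group smaller but does not close the gap. These are efforts and permissions, and under 3.8.2 collection on this protocol ends once a patient is off-study, which progression or a new cancer therapy brings about.

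The text can also be read so that a patient who has not yet received dose 5 on Day 56 is still among those who must return. That is a fair reading, and it is why the point here is lack of clarity. A reader might infer that no second-course patient is ever scanned at Day 56; the wording does not establish that.

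A reader might also infer a loss of power, because 80.3% is barely above 80%. The documents do not support a figure. They give neither the share taking a second course nor the fraction of responses missed, and course 2 may add responses. In addition, partial response is judged against baseline, so a tumour that has regrown from an unseen low may still qualify at Day 126.

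Finally, a reader might see 3.1.3, 3.6.1 and 3.8.1 as contradicting each other over progression before doses 5 to 8. They do not: progression can be found clinically or at an unscheduled assessment.

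**Conclusion.** The point holds as a minor one. Because of the late scan, 8.3.2 as worded can remove from the decision denominator a patient who had a full course and most likely did not respond. On that assumption the observed rate can only move up. The size is 1.0 percentage point of type I error for one such patient per cohort and 1.9 points for two, so the stated 10% limit is not breached. The intention-to-treat analysis reports a wider population but does not change the two-stage rule.

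Separately, 3.6.1 should say what happens at Day 56 while the second-course decision is open. Some transient responses may go unseen in the meantime, in unknown number. With one mechanism raising the rate, another lowering it and no second-course share given, no net direction of bias can be stated.

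**What to change.** 1. In 8.3.2, count in the response denominator every patient with measurable disease at baseline who completed at least one course (four vaccination cycles, as in 3.1.3), whether or not a second was started. A patient with no post-baseline response assessment counts as a non-responder. This treats one-course and two-course patients alike. Cost: wording only, and possibly a slightly lower reported response rate.

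2. In 3.6.1, footnote 2 of 3.7 and 6.3, state that the Day 56 evaluation with imaging applies to any patient who has not received dose 5 by that visit. Keep the evaluation two weeks after the last vaccination, and derive best overall response from all scans with the existing 4-week confirmation. Cost: amendment wording and one scan for the second-course subset, which one-course patients already have, plus the confirmatory scan that 6.3 already requires if a response is seen.

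The sponsor may also wish to clarify how progression under 3.8.1 is assessed before doses 5 to 8, since an earlier scan could reveal it sooner. No rule on who continues treatment is proposed here.

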3.6.2 Subsequent Follow-up Evaluations

All patients will return to the NIH Clinical Center for their second follow-up evaluation one month (± 5 days) after the first follow-up evaluation. Subsequent follow-up evaluations will take place every 1-2 months for the first year, and then annually for up to five years or until clinically proven progressive disease, whichever comes first. Patients will be co-enrolled and followed on the NCI-SB long-term follow-up protocol 09-C-0161 (Follow-up Protocol for Subjects Previously Enrolled on NCI Surgery Branch Studies). As noted in Section **3.6.1**, additional apheresis may be performed only at the first follow-up evaluation. It will not be performed at any other post-treatment evaluations.

Note: Patients may be seen more frequently as clinically indicated. Patients who are unable or unwilling to return for follow-up evaluations may be followed via phone or email contact. Patients may be asked to send laboratory, imaging, and physician exam reports performed by their treating physician.

At each scheduled follow-up evaluation, patients will undergo:

- Physical examination, including ECOG (see Appendix B)
- Weight and vital signs
- Toxicity assessment, including a review of systems
- CBC w/differential
- Acute Care Panel (sodium, potassium, chloride, bicarbonate, creatinine, glucose, BUN), Hepatic Panel (alkaline phosphatase, AST, ALT, total bilirubin, direct bilirubin), Mineral Panel (albumin, calcium, magnesium, phosphorus), Uric acid, Creatinine kinase, Lactate dehydrogenase, Total protein
- Lymphocyte phenotyping (TBNK)
- β-HCG pregnancy test (serum or urine) on all women of child-bearing potential (complete at all follow-up evaluations within 120 days after the last vaccine)
- Research samples, as described in Section **5.3**. Approximately 72 mL of blood will be obtained at each follow-up visit. PBMC will be cryopreserved so that immunologic testing may be performed. This will be performed on protocol 03-C-0277.
- Imaging studies as performed at baseline to determine tumor response. If clinically indicated, other scans or x-rays may be performed, e.g. brain MRI, bone scan.

STUDY ASSESSMENT CALENDAR 3.7

		Screening		Baseline	ine	S-nO	study/Cou	On-Study/Course of Treatment	atment	Doct Two	Doct Turotmont Follow un
	(Prior to Pa	Prior to Part Two registrati	istration)	(Prior to first vaccine)	t vaccine)		(1 vaccin	$(1 \text{ vaccine} = 1 \text{ cycle})^1$	e) ¹	L USU- 116	aunent ronow-up
	Within 3	Within	Within	Within 7	Within	Day		Day 14 Day 28 Day 42	Day 42	Day 56 ²	Subsequent
Assessments	Months	4 Weeks	7 Days	Days	2 Days	0	(±5 d)	(±5 d)	(±5 d)	(±5 d)	Follow-up Visits ³
Confirmation of diagnosis by NCI	Λ										
Lab of Pathology ⁴	<										
Medical history ⁵		Х									
Physical exam		Х	Х	Х			Х	Х	Х	Х	Х
Performance status (ECOG) ⁶			Х	Х			Х	Х	Х	Х	Х
Weight			Х	Х			Х	Х	Х	Х	Х
Vital signs ⁷			Х	Х		Х	Х	Х	Х	Х	Х
β-HCG pregnancy test ⁸			Х	Х			Х	Х	Х	Х	X^9
Urinalysis ¹⁰			Х	Х							
EKG				Х							
Toxicity assessment ¹¹					X^{12}		Х	Х	Х	Х	Х
Serology											

1 Assessments must be performed within 2 days prior to each vaccination on Days 14, 28, & 42. Patients may receive a 2nd course of treatment for a total of 8 cycles.

2 If a patient receives a second course of four vaccines, the first follow-up evaluation will be two weeks (\pm 5 days) after the eighth vaccination.

3 All patients will return to the NIH Clinical Center for their second follow-up evaluation one month (\pm 5 days) after the first follow-up evaluation. Subsequent followup evaluations will take place every 1-2 months for the first year, and then annually for up to five years or until clinically proven progressive disease, whichever comes first. Patients may be seen more frequently as clinically indicated. Patients who are unable or unwilling to return for follow-up evaluations may be followed via phone

4 Confirmation of diagnosis of metastatic melanoma, gastrointestinal, or genitourinary cancer. Testing is permitted to be conducted at any time prior to Part Two or email contact. Patients may be asked to send laboratory, imaging, and physician exam reports performed by their treating physician. registration.

5 Patient history may be obtained within 8 weeks prior to Part Two registration.

6 ECOG of 0 or 1 (see Appendix B).

7 After each vaccination, vital signs will be monitored hourly (\pm 15 minutes) for two hours. The post-administration monitoring period may be adjusted by the PI. 8 Serum or urine; on all women of child-bearing potential

9 Complete at all follow-up evaluations within 120 days after the last vaccine.

10 With culture if indicated.

11 Including a review of systems.

12 Review of baseline symptoms.

Abbreviated Title: mRNA-Based, Cancer Vaccine	
Cancer	
-Based,	Vaucion Data: January 22 2010
mRNA	C
Title:	or Law
iated	, Dat
Abbrev	Varcion

6
-
0
2019
23,
\sim
January
Date:
Version

		Screening		Baseline	ine	On-S	tudy/Cou	On-Study/Course of Treatment	eatment	D t T	
	(Prior to Pa	(Prior to Part Two registration)	istration)	(Prior to first vaccine)			(1 vaccin	$1 \text{ vaccine} = 1 \text{ cycle})^1$	$e)^1$	LOSU-1 LE	rost- i reatiment romow-up
	Within 3	Within	Within	Within 7		Day	Day 14	Day 14 Day 28	Day 42	Day 56 ²	Subsequent
Assessments	Months	4 Weeks	7 Days	Days	2 Days	0	(±5 d)	(±5 d)		(±5 d)	Follow-up Visits ³
HIV antibody titer, HBsAg, anti-	Х										
Anti-CMV antibody titer, HSV and VZV EBV nanel ¹³				Х							
Laboratory Procedures											
CBC w/differential			Х	Х			Х	Х	Х	Х	X
Blood chemistries ¹⁴			Х	Х			Х	Х	Х	Х	X
PT-INR/PTT				Х							
Lymphocyte phenotyping (TBNK)			Х		Х					Х	Х
Additional apheresis ¹⁵										Х	
Correlatives ¹⁶											
CPT tubes (SB-CPF)					Х		Х	Х	Х	Х	X
SST tubes ([name] Lab)					Х		Х	Х	Х	Х	Х
Imaging											
CT, MRI, PET, and/or		\mathbf{X}^{17}		X^{18}						X^{19}	\mathbf{X}^{19}
photography		¥7								×.	
Chest x-ray				Х							
Treatment/Intervention											
NCI-4650 mRNA vaccine ²⁰						Х	Х	Х	Х		

¹³ Patients who are known to be positive do not need to be retested. May be performed within 3 months prior to Part Two registration.

14 Screening: Creatinine, ALT/GPT, AST/GOT, Total bilirubin. All other times: Acute Care Panel (sodium, potassium, chloride, bicarbonate, creatinine, glucose, BUN), Hepatic Panel (alkaline phosphatase, AST, ALT, total bilirubin, direct bilirubin), Mineral Panel (albumin, calcium, magnesium, phosphorus), Uric acid, Creatinine kinase, Lactate dehydrogenase, Total protein.

15 A 5-liter apheresis may be performed. If the patient is unable to undergo apheresis, approximately 96 mL of blood may be obtained. This will be performed on protocol 03-C-0277, and will only be performed at the first follow-up evaluation.

16 Research samples, as described in Section 5.3.

17 Imaging evaluation to determine baseline disease status.

18 Repeat imaging if not performed within 4 weeks of Day 0.

19 As performed at baseline to determine tumor response. If clinically indicated, other scans or x-rays may be performed, e.g., brain MRI, bone scan. 20 Administered intramuscularly.

